5.4.1.2 Consumption of nonacog beta pegol for treatment of bleeding episodes

This endpoint will be evaluated based on data from both Arm A and Arm B.

The number of injections per bleed will be summarised and listed.

The number of IU/Kg per bleed will be summarised and listed.

5.4.1.3 Consumption of nonacog beta pegol for PPX treatment

This endpoint will be evaluated based on data from Arm B only.

The number of injections for PPX treatment (i.e. excluding treatment of breakthrough bleeds) will be summarised and listed.

The number of IU/Kg per year will be summarised and listed.

5.4.1.4 FIX trough levels during PPX treatment

This endpoint will be evaluated based on data from Arm B only.

The FIX trough and recovery levels will be analysed by a mixed model on the log-transformed plasma FIX activity with patient as a random effect. The mean trough and recovery levels will be presented back-transformed to the natural scale together with the 95% confidence interval.

The following rules will be implemented for the analysis of trough and recovery levels:

- Pre-dose and post-dose values will be excluded if post-dose activity is \leq pre-dose activity
- Pre-dose and post-dose values taken less than 5 days or more than 9 days after last dose will be excluded
- Pre-dose and post-dose values taken less than twice the PPX treatment interval (14 days) after last treatment of a bleeding episode will be excluded
- Pre-dose and post-dose values taken within 2 weeks after surgery will be excluded
- Pre-dose and post-dose values taken in relation to the first exposure will be excluded
- FIX activity measured in defrosted plasma samples will be excluded

Furthermore, trough and recovery (30 minutes post-dose) levels measured at scheduled visits will be summarised and listed. Incremental recovery will be calculated and presented in summary tables and plots.

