### **8.6.2 FIX inhibitors**

All patients will be examined for the development of FIX inhibitors at scheduled visits (see Section [1.2](#)). Blood samples for analysis of FIX inhibitors will be collected on the day of surgery and again upon return to assigned treatment at the end of the surgery period.

Blood samples for measurement of inhibitors towards FIX will be analysed according to the Nijmegen modification of the Bethesda assay.

If FIX inhibitor development is suspected (e.g. increased number of bleeding episodes, bleeding episodes difficult to treat, nonacog beta pegol recovery and trough levels below expected values) during the trial, additional inhibitor tests can be taken. All inhibitor tests must be analysed by the central laboratory.

A positive inhibitor test is defined as  $\geq 0.6$  BU. If a previously inhibitor negative patient has a positive inhibitor test ( $\geq 0.6$  BU), the patient will be requested to visit the site for additional sampling preferably within 2 weeks. These samples should preferably be taken prior to any change of treatment. In addition, the following tests should be performed:

- FIX trough (pre-dose)
- FIX recovery (30 min post-dose)
- Lupus anticoagulant.

A patient is verified inhibitor positive if the patient has been tested positive for inhibitors ( $\geq 0.6$  BU) at two consecutive tests performed at the central laboratory preferably with no more than 2 weeks between the tests.

Inhibitor positive patients must be discontinued from trial treatment if FIX inhibitors  $>5$  BU or if FIX inhibitors  $\geq 0.6$  and  $\leq 5$  BU that makes treatment (prophylaxis and/or treatment of bleeding episodes) with nonacog beta pegol clinically ineffective, by discontinuing trial product and attending the discontinuation of treatment visit (visit 10A) within 1 week after the result is available.

If the second (confirmatory) inhibitor test is positive and  $\leq 5$  BU and the investigator judges that the inhibitor does not clinically interfere with nonacog beta pegol treatment (prophylaxis and/or

treatment of bleeding episodes), the patient can stay in the trial and continue treatment as per protocol.

For patients discontinued from treatment with nonacog beta pegol, the follow-up visit (Visit 11) must be scheduled 30 +5 days after the discontinuation of treatment, and additional follow-up contact(s) (e.g. phone calls) may be arranged as long as clinically warranted up to 3 months after Visit 11.

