5.1 General considerations

Novo Nordisk will be responsible for the statistical analyses. The SAP will be finalised prior to first patient first visit.

Unless otherwise stated, all endpoints will be presented in total and by treatment regimen/period as applicable (on-demand period in Arm A; PPX period in Arm A; and Arm B [PPX]).

Summaries for continuous endpoints will include total number (N), mean (standard deviation), median and min/max and for pharmacokinetic endpoints also geometric mean and coefficient of variation (CV%). Summaries for categorical endpoints will include total number (N), number for each outcome category (n) and percentage for each outcome category (%).

FIX activities below lower limit of quantification (LLOQ) will be set to half the value of the LLOQ.

All bleeding endpoints will be evaluated based on bleeding episodes requiring treatment with haemostatic drugs. Non-treatment requiring bleeding episodes will only be listed. Bleeding episodes in relation to major surgery will also only be listed, i.e. not included in the analysis of bleeding endpoints.

Multiple bleeding locations occurring from the same event (e.g. due to a bicycle accident) or at the same time point will be counted as one bleeding episode and only one haemostatic response will be considered for the bleeding episode. In case different responses were registered for different bleeding locations in such a bleeding episode, the worst response will be used in the analysis.

A re-bleed is defined as a worsening of symptoms in the same location after an initial period of improvement, either on treatment or within 72 hours after stopping treatment. If a bleed occurs in the same location later than 72 hours after stopping the treatment it is considered a new bleed. Re-bleeds will only be considered for joint bleeds since the specific location for other bleeds e.g. in subcutaneous are not captured in the database.

In the sub-analyses of annualised bleeding rate (ABR) where there are less than 5 patients or no bleedings in a sub-group, the confidence interval will not be calculated.

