5.4 Secondary endpoints analysis

5.4.1 Secondary efficacy endpoints

Endpoint title	Time frame	Unit
Number of treated bleeding episodes during PPX treatment (Arm B only)	From start of treatment (week 0) until end of treatment (week 50)	Count
Consumption of nonacog beta pegol for treatment of bleeding episodes	From start of treatment (week 0) until end of treatment (up to week 50)	IU/kg per bleed

Consumption of nonacog beta pegol for PPX treatment (Arm B only)	From start of treatment (week 0) until end of treatment (week 50)	IU/kg per year
FIX trough levels during PPX treatment (Arm B only)	From start of treatment (week 0) until end of treatment (week 50)	IU/mL

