λ_z	Single-dose: 0-168 hours post-injection at week 0 Steady-state: 0-168 hours post-injection at week 12	1/h	Terminal elimination rate constant. The terminal elimination rate constant will be estimated using linear regression on the terminal part of the log(activity) versus time profile.

Single-dose pharmacokinetics will be based on the pharmacokinetic session at Visit 2, and steady-state pharmacokinetics will be based on the pharmacokinetic session at Visit 5.

The pharmacokinetic parameters will be calculated using plasma FIX activity obtained from one-stage clotting assay. The pharmacokinetic parameters will be derived according to a non-compartmental method, as described in [Table 2](#). The actual time points will be used in the calculations.

If any profiles and/or individual plasma FIX activities are excluded from the primary pharmacokinetic analysis, a sensitivity pharmacokinetic analysis will also be performed and reported based on all observed data. The primary pharmacokinetic analysis is based on the FAS excluding outliers.

Which specific pharmacokinetic data points and profiles that will be excluded will be defined prior to database lock. Profiles with pre-dose FIX activity >5% at Visit 2 (possibly indicating inadequate wash out) and profiles that are not indicative of a normal i.v. injection (i.e. clearly increasing plasma FIX activity initially) should be excluded. If a patient is treated with an additional dose during the pharmacokinetic session, the plasma concentrations after the occurrence will then be excluded. Furthermore, if the pharmacokinetic profile shows indications of an additional dose (e.g. clearly increased plasma FIX activity), the plasma concentrations after the occurrence will then also be excluded.

Individual and mean pharmacokinetic profiles will be presented graphically.

Furthermore, the mean pharmacokinetic endpoints will be summarised and individual pharmacokinetic endpoints will be listed.

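### The trough and recovery model drops every pre/post pair with no measured rise in FIX activity, so true non-recovery is partly or wholly left out of the modelled mean and its confidence interval

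*SAP*

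**What the plan says.** SAP 5.4.1.4 specifies the model: "The FIX trough and recovery levels will be analysed by a mixed model on the log-transformed plasma FIX activity with patient as a random effect". Its back-transformed mean is reported with a 95% confidence interval. Trough during prophylaxis is a named secondary efficacy endpoint in Arm B; recovery is modelled alongside it.

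Six exclusions follow, introduced by "The following rules will be implemented for the analysis of trough and recovery levels". The first reads "Pre-dose and post-dose values will be excluded if post-dose activity is" no higher than pre-dose activity. Both members of the pair go. Protocol 9.4.3.2 has the same rule. Neither document gives a reason for it, asks for evidence of an error, or makes an exception.

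Three other provisions bear on it:

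- SAP 5.1: "FIX activities below lower limit of quantification (LLOQ) will be set to half the value of the LLOQ".
- Protocol 8.6.2 lists among the grounds for suspecting an inhibitor "nonacog beta pegol recovery and trough levels below expected values".
- SAP 5.4.3 provides that, if data are excluded from the pharmacokinetic analysis, "a sensitivity pharmacokinetic analysis will also be performed and reported based on all observed data". Section 5.4.1.4 has no counterpart.

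Section 5.4.1.4 also promises descriptive output: "Furthermore, trough and recovery (30 minutes post-dose) levels measured at scheduled visits will be summarised and listed". It does not say whether the exclusions apply there.

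**The concern.** The other five exclusions turn on time since the last dose, recent bleed treatment, recent surgery, first exposure, or sample handling. Only this one selects on the measured result. A pair with no rise after a dose may be a swapped sample, but it may also be what a neutralising inhibitor produces, and the rule cannot tell the two apart. The pre-dose value, which is the trough endpoint itself, is deleted because of what the post-dose sample showed.

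At stake is what the modelled figures mean. They describe levels at visits where a rise was measured, not levels on prophylaxis in all eligible samples. Protocol 4.3 refers to a 15% mean trough as a theoretical threshold, and protocol 4.2 plans a comparison with the global pivotal trial, so the modelled trough will be read as an efficacy result.

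**Working it through.** The plan states no figure to reproduce. The rule, the half-LLOQ substitution, the model and the 15 Arm B patients come from the documents. LLOQ, assay noise, expected levels and failure rate do not, so every size below is illustrative.

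**1. The rule applied to single pairs** (IU/mL, LLOQ taken as 0.01)

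| Pre | Post | After substitution | Result |
|---|---|---|---|
| 0.20 | 0.90 | unchanged | kept |
| 0.20 | 0.20 | unchanged | dropped |
| 0.20 | 0.15 | unchanged | dropped |
| 0.002 | 0.004 | 0.005, 0.005 | dropped (tie) |
| 0.002 | 0.012 | 0.005, 0.012 | kept |

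Pairs with both values below LLOQ always leave. A small positive rise stays.

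**2. How often noise alone triggers the rule.** With lognormal assay error, P(post ≤ pre) = Φ(−ln(post/pre) / (σ√2)), where σ² = ln(1 + CV²) and post and pre are the true levels.

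- *Normal recovery.* Take trough 0.27, rise 0.4, CV 20%. Then σ = 0.198, ln(0.67/0.27) = 0.909, and Φ(−0.909/0.280) ≈ 0.0006. Over troughs of 0.15–0.27 and rises of 0.4–0.9, this 0.06% is the largest value at CV up to 20%. At CV 30% the worst case is 1.4%. Noise therefore seldom triggers the rule in a patient who responds; what it catches is mainly handling errors and true non-recovery.
- *No true rise, detectable activity.* The log ratio is 0, so Φ(0) = 0.50. Simulation of 200,000 pairs at 5%, 10% and 20% noise also gave 0.50. The mean rise was 0 over all pairs, but +0.014 to +0.057 IU/mL among those retained.

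**3. Effect on the modelled mean.** Assume 15 patients, 8 visits each, trough about 0.25 and recovery about 1.0. One patient leaves after 4 visits, with both values below LLOQ at the last. A random-intercept REML model on log FIX (200 replicates, LLOQ 0.01) gave:

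| | All pairs | With the rule | Ratio |
|---|---|---|---|
| Trough | 0.238 | 0.252 | 1.059 |
| Recovery | 0.943 | 1.011 | 1.072 |

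The log-scale standard error of the trough was 0.086 with all pairs and 0.066 with the rule. Over LLOQ 0.01–0.02 the excess is roughly 5–6% for trough and 6–7% for recovery.

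*Hand check at LLOQ 0.01.* The log gap for trough is ln(0.25/0.005) = 3.91. Weighting all 14 × 8 + 4 = 116 pairs equally gives 3.91/116 = 0.034, or 3.4%. Weighting patients equally gives 3.91/(15 × 4) = 0.065, or 6.7%. For recovery, ln(1.0/0.005) = 5.30 gives 5.30/116 = 0.046 (4.7%) and 5.30/60 = 0.088 (9.2%). A random-intercept model weights between these extremes, and both simulated results lie inside.

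*Second approximation.* One failed pair among 15 × 7 changes the geometric mean by ((LLOQ/2)/level)^(1/105) − 1. With trough 0.15–0.27, rise 0.7 and LLOQ 0.005–0.02, keeping the pair lowers trough by 2.5–4.4% and recovery by 4.1–5.5%.

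**4. Two affected visits.** At LLOQ 0.01, two of four visits give 0.251/0.222 = 1.13 for trough and 1.007/0.855 = 1.18 for recovery. Two of three give 0.251/0.213 = 1.18 and 1.007/0.804 = 1.25.

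**The case against.** Much of the case for leaving the rule alone has force.

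- *It has a plausible use.* A swapped pair often shows only through its reversed values. Kept in (pre 0.9, post 0.2, say), it would inflate the trough. Restricting the main exclusion to documented errors would let such pairs through. This stands and is a reason to retain the rule as a screen.
- *The inhibitor procedures limit exposure.* Under protocol 8.6.2 a positive test prompts a retest, preferably within 2 weeks. If trial product has to stop, Visit 10A follows within 1 week of the result, and protocol 7.1 ends FIX activity sampling after that. Scheduled visits are 4 to 8 weeks apart, so a second affected pair would probably have to come from the retest. Patients who continue have an inhibitor of at most 5 BU that is judged not to interfere clinically. This stands against the figures in step 4.
- *Other exclusions overlap.* Pairs within 14 days of bleed treatment go anyway, and a patient losing response may be treating bleeds. This stands; the share due to this rule alone may be smaller than calculated.
- *The calculation leans on substitution.* Half-LLOQ values lie 3 to 4 log units below the assumed trough and largely drive the change in standard error. This also stands.
- *Loss of response is reported elsewhere.* By-visit summaries, listings, incremental recovery and the inhibitor endpoint may all show it. This stands only in part: section 5.4.1.4 does not say whether its descriptive outputs include the dropped pairs, and none of these outputs corrects the modelled mean and interval.
- *Nothing confirmatory depends on it.* The trial tests no hypothesis and the estimate is descriptive. This stands and keeps the point minor.

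**Conclusion.** The point holds, at minor weight. A rule based on the result itself removes every pair with no measured rise, without evidence of error, and nothing planned shows what the model would give with those pairs kept. Recovery is biased upward whenever true non-recovery is dropped. Trough is biased upward when the lost pre-dose value is low. One fully neutralised patient with one affected visit gives roughly 5–6% and 6–7%, on assumed levels, LLOQ and visit counts. With no loss of recovery the effect is nil.

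A reader might infer more, and the documents do not support it:

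- *That complete failure of recovery can never appear in the model.* About half of the no-rise pairs with detectable activity stay in, with post-dose values near trough that pull mean recovery down. Partial loss of recovery also stays. Only pairs with both values below LLOQ are certain to go.
- *That the trough is always overstated.* If the dropped pre-dose value is high, the direction can reverse.
- *That errors of 18% and 25% are to be expected.* Those need two fully neutralised visits in one patient, which fits poorly with the retesting and stopping provisions.
- *That loss of response is hidden from the report.* The inhibitor endpoint is analysed separately, and the plan does not say that the listings omit these values.

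**What to change.** In SAP 5.4.1.4 and protocol 9.4.3.2:

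1. Keep the rule in the main analysis, stating that it screens for swapped or mishandled samples.
2. Do not apply it to pairs from a patient with a FIX inhibitor test of 0.6 BU or more at that or an adjacent visit. The other five exclusions still apply to those pairs. Inhibitor samples are already scheduled throughout treatment.
3. Add one sensitivity run of the same mixed model that keeps every pair with post-dose activity at or below pre-dose, mirroring SAP 5.4.3.
4. Report the number of pairs and of patients removed by this rule, and say whether the exclusions apply to the by-visit summaries and incremental recovery.

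The cost is a few sentences and one extra model run on data already collected. The drawback is that the sensitivity estimate may include undetected sample swaps, so it should be read with the count of excluded pairs.

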In Arm B, starting with the first dose of trial product at Visit 2, patients will undergo a PPX treatment period lasting until 50 EDs to nonacog beta pegol (including treatment of breakthrough bleeds) and 50 weeks in trial (including Visits 3-9 at 4, 8, 12, 20, 28, 36 and 44 weeks). One single-dose and one steady-state pharmacokinetic profile (168 hours) will be obtained in patients in Arm B. The single-dose pharmacokinetic profile will start at first dosing (Visit 2), while the steady-state pharmacokinetic profile will be obtained at Visit 5.

Both treatment arms will end with an end of treatment visit (Visit 10), and an end of trial (follow-up) visit (Visit 11) is placed 30 days after the end of treatment visit.

Major and minor surgery is allowed in the trial.

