### 2.2 Nonacog beta pegol

Nonacog beta pegol is a glycopegylated recombinant human FIX with an extended half-life, which was developed to offer a more effective and less burdensome treatment compared to standard FIX products. An improved overall pharmacokinetic profile provides the ability to sustain higher FIX levels than with standard therapies. Thus, nonacog beta pegol has the potential to improve prophylaxis and simplify management of bleeds as well as perioperative haemostatic control in patients with haemophilia B.

The clinical development programme for nonacog beta pegol was initiated in August 2009. Five trials have been completed in previously treated adolescent and adult patients: two phase 1 trials in adult patients (Trials 3639 and 4260) and three phase 3 trials in adolescent or adult patients (Trials 3747, 3773 and 3775). In addition, the main phase of Trial 3774 in previously treated paediatric patients has also been completed, whereas the extension phase is still ongoing. Finally, Trial 3895 in previously untreated paediatric patients is ongoing. In the phase 1 trials, 31 patients have been exposed to nonacog beta pegol. In Trials 3747, 3773, 3775 and 3774 (main phase), 105 unique previously treated patients have been exposed to nonacog beta pegol with a total of 8,785 exposure days (EDs).

The phase 1 Trial 3639 comparing nonacog beta pegol and patients' previous FIX product showed that nonacog beta pegol has a 5-fold prolonged half-life ( $t_{1/2}$ ) compared to marketed plasma-derived and recombinant standard half-life FIX products. In Trial 4260 comparing the single-dose pharmacokinetics of nonacog beta pegol with ALPROLIX®, both at a dose of 50 IU/kg, a statistically significantly longer  $t_{1/2}$  (by 22%) was observed for nonacog beta pegol vs. ALPROLIX® (estimated ratio [95% confidence interval] nonacog beta pegol/ALPROLIX® 1.22 [1.09; 1.35]).

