#### **4.1.3 Prophylaxis**

During PPX treatment, one single bolus dose of 40 IU/kg nonacog beta pegol will be administered i.v. once weekly. If a dose for treatment of bleeding is taken, the next PPX dose should still be taken on the planned day.

Additional doses of nonacog beta pegol can be administered if a patient experiences a treatment-requiring bleeding episode (see Section [4.1.4](#)) or in case of surgery (see Section [4.1.5](#)).

If a bleeding episode occurs on a planned PPX dosing day before administration of the PPX dose, or if a bleeding episode extends into such a day, the bleeding episode must be treated with the full PPX dose (this dose should be recorded as treatment of a bleeding episode). The patient should always follow the original PPX dosing scheme unless a dose has already been given to treat a bleeding episode during the same day.

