## **8.5 Pharmacokinetics**

Patients in Arm B (PPX) will be administered a single i.v. bolus injection of 40 IU/kg of nonacog beta pegol at Visits 2 and 5. The pharmacokinetic sessions extend over 168 hours after dosing. After completion of the pharmacokinetic sessions, the patients will return to PPX treatment with the next visit in line.

Patients must not have received current FIX product for at least 96 hours prior to the administration of trial product for the single-dose pharmacokinetic session at Visit 2 (i.e. a wash-out period of at least 96 hours must be applied before Visit 2).

There is no wash-out period for the steady-state pharmacokinetic session at Visit 5. However, administration of trial product at Visit 5 should be approximately 168 hours after the previous nonacog beta pegol dose.

Patients must not be actively bleeding during the pharmacokinetic sessions.

The pharmacokinetic endpoints (see Section [3.2.2.3](#)) will be based on assessments performed from 1 hour prior to and up to 168 hours after administration of nonacog beta pegol at Visits 2 (single-dose pharmacokinetic assessments) and 5 (steady-state pharmacokinetic assessments) (see the flowchart for pharmacokinetic assessments in [Table 1-1](#)).

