### 9.2 Sample size determination

No formal sample size calculations have been performed. Based on meeting communication with CDE, a total number of 24 Chinese patients to complete this trial is assessed to be sufficient to evaluate efficacy and safety in the Chinese population, considering that data are also available from the global pivotal trial NN7999-3747, which included Asian patients. In order to account for withdrawn patients, 30 patients will be started on trial product (15 patients in Arm A [on-demand/PPX] and 15 patients in Arm B [PPX]).

All 15 patients in Arm B will participate in the pharmacokinetic evaluation to ensure that at least 12 patients will complete single-dose and steady-state pharmacokinetic profiles.

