### **FIX trough levels during PPX treatment**

This endpoint will be evaluated based on data from Arm B only.

The FIX trough and recovery levels will be analysed by a mixed model on the log-transformed plasma FIX activity with patient as a random effect. The mean trough and recovery levels will be presented back-transformed to the natural scale together with the 95% confidence interval.

The following rules will be implemented for the analysis of trough and recovery levels:

- Pre-dose and post-dose values will be excluded if post-dose activity is  $\leq$  pre-dose activity.
- Pre-dose and post-dose values taken less than 5 days or more than 9 days after last dose will be excluded.
- Pre-dose and post-dose values taken less than twice the PPX treatment interval (14 days) after last treatment of a bleeding episode will be excluded.
- Pre-dose and post-dose values taken within 2 weeks after surgery will be excluded.
- Pre-dose and post-dose values taken in relation to the first exposure will be excluded.
- FIX activity measured in defrosted plasma samples will be excluded.

Furthermore, trough and recovery (30 minutes post-dose) levels measured at scheduled visits will be summarised and listed. Incremental recovery will be calculated and presented in summary tables and plots.

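### The Arm B FIX trough model has no term for time since dose, so early or late sampling on average would move the mean trough away from its 7-day value

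*SAP*

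**What the plan says.** SAP 5.4.1.4 has Arm B trough and recovery levels "analysed by a mixed model on the log-transformed plasma FIX activity with patient as a random effect". Protocol 9.4.3.2 describes the same model. The result is a back-transformed mean with a 95% confidence interval. No fixed effect for time since dose, visit or nominal time is named, and no narrower-window sensitivity analysis is planned.

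Both documents apply the same timing rule: "Pre-dose and post-dose values taken less than 5 days or more than 9 days after last dose will be excluded". Further exclusions cover recent bleeds, recent surgery, first exposure, defrosted samples, and pairs whose post-dose value does not exceed the pre-dose value.

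The intended interval is 7 days, since in prophylaxis "one single bolus dose of 40 IU/kg nonacog beta pegol will be administered i.v. once weekly" (protocol 4.1.3). An explicit interval before a visit is given only for the steady-state pharmacokinetic session: "administration of trial product at Visit 5 should be approximately 168 hours after the previous nonacog beta pegol dose" (protocol 8.5). Actual sampling times enter the calculation of the pharmacokinetic parameters (SAP 5.4.3, protocol 9.4.3.4), but neither document uses them in the trough model.

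**The concern.** A pre-dose value at day 5 and one at day 9 do not measure the same quantity. With an intercept and a patient effect only, any average departure from 7 days goes into the estimated mean, and scatter around 7 days goes into the variance terms.

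FIX trough is a named secondary efficacy endpoint, and protocol 4.1 calls FIX activity a surrogate for efficacy. The protocol cites 15% as a proposed threshold (2.1), reports mean troughs above it in earlier trials (4.3), and plans to compare this trial with the global pivotal trial (4.2). If the mean partly reflects the sampling day, a difference from earlier data could be one of timing rather than of patients.

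**Working it through.** The plan gives no precision or sample-size figure for this endpoint, so there is none to reproduce.

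**Inputs from the documents**
- Retained window 5 to 9 days (120 to 216 h), centred on the planned 168 h.
- Patients, n = 12 to 15: "All 15 patients in Arm B will participate in the pharmacokinetic evaluation to ensure that at least 12 patients will complete" both profiles (protocol 9.2).
- About m = 7 samples per patient, from the treatment-period visits: "including Visits 3-9 at 4, 8, 12, 20, 28, 36 and 44 weeks" (protocol synopsis). Visit 2 drops out as first exposure.
- Half-life: only a relative statement, "nonacog beta pegol has a 5-fold prolonged half-life" compared with standard products (protocol 2.2).

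**Assumptions**
- Half-life h of 60 to 120 h, central value 90 h.
- First-order decay over the window, ignoring the patient's own FIX level (at most 2% by inclusion criterion).
- Log-scale SDs of 0.2-0.4 between patients (sb) and 0.15-0.25 within patients (sw).

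**1. Dependence on sampling day.** Activity at time t relative to 168 h is 2^(-(t-168)/h).

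| Half-life | Day 5 | Day 9 | Mean 1 day early | Mean 1 day late |
|---|---|---|---|---|
| 60 h | x1.74 | x0.57 | +32% | -24% |
| 90 h | x1.45 | x0.69 | +20% | -17% |
| 120 h | x1.32 | x0.76 | +15% | -13% |

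A level of 15% at day 7 would read about 20-26% at day 5 and 9-11% at day 9. These are the window edges, not expected errors. The shift columns scale with the size of the lean: half a day early gives 2^(12/h) - 1, or +15%, +10% and +7%.

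**2. Effect on precision when timing is symmetric.** With k = ln2/h and timing SD st,

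SE of the mean log trough = sqrt((sb² + (sw² + k²·st²)/m)/n).

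Take h = 90 h, sb = 0.3, sw = 0.2, n = 15, m = 7:
- No timing variation: sqrt((0.09 + 0.04/7)/15) = 0.0799.
- Timing SD 0.8 day (19.2 h): k·st = 0.148; sqrt((0.09 + (0.04 + 0.0219)/7)/15) = 0.0812, or +1.6%.
- Uniform over 5-9 days (SD 96/√12 = 27.7 h): k·st = 0.213; sqrt((0.09 + (0.04 + 0.0455)/7)/15) = 0.0826, or +3.3%.

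Over the assumed SDs, the uniform case adds 2-7% at 90 h. Over all assumed half-lives it adds 1-16%, the top figure coming from the shortest half-life with the smallest SDs. Timing within ±1 day adds 0.3-4%. Between-patient variation dominates.

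**3. Simulated fits** (same settings, true 7-day level 0.200 IU/mL, 200 runs per scenario), without and with a linear term for days since dose minus 7:

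| Timing | Mean without | Mean with | SE without | SE with |
|---|---|---|---|---|
| Uniform 5-9 days | 0.199 | 0.198 | 0.079 | 0.076 |
| ±1 day around day 7 | 0.200 | 0.200 | 0.080 | 0.079 |
| ±1 day around day 6.5 | 0.219 | 0.199 | 0.079 | 0.080 |
| ±1 day around day 6 | 0.243 | 0.201 | 0.078 | 0.087 |

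Some fits gave convergence warnings; the closed-form results agree with them. With off-centre timing, the covariate removes the bias and makes the interval somewhat wider.

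**The case against.** The best counter-argument is that timing is already controlled. The 5-9 day rule is pre-specified and symmetric around the planned interval. Patients are told to keep to the weekly schedule (protocol 4.1.3), and Appendix 2 requires sample timing relative to dosing to be respected. A steady-state 168 h level is planned for the same arm among the pharmacokinetic parameters. The trough endpoint is not defined as the level at exactly 168 h, and the pre-dose level under weekly dosing as delivered is a legitimate quantity. All of this stands, and it is why the planned mean should stay.

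Three stronger readings are tempting but unsupported:
- **The ±7-day visit windows imply that intervals spread over 5-9 days.** A visit window is not a dosing-interval window. A visit moved by a week can fall on another dosing day with the interval unchanged. The documents show no lean in either direction.
- **The trough estimate is materially noisier than it need be.** With symmetric timing, independent across visits, the loss at 90 h is a few percent. Larger losses (13-43% in SE at 90 h) require each patient always to be sampled at his own off-centre time, which nothing in the documents indicates.
- **The time-adjusted mean should replace the planned one at no cost.** The adjusted SE rises when timing is off-centre (0.087 against 0.078). How the pivotal trial's troughs were analysed is not shown, so replacement could reduce comparability.

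Clock times are required for doses given at the site (protocol 6.4). For home doses neither that section nor the diary section (8.7) states them, so a covariate in hours may not be available throughout.

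The objection does not remove the dependence on an average lean. Symmetric limits do not make the retained values symmetric, and the 168 h pharmacokinetic value comes from one session rather than from troughs over the whole treatment period.

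**Conclusion.** The point holds as one about possible bias. As written, the model would carry an average early or late lean in sampling straight into the mean trough: up 15-32% for one day early, down 13-24% for one day late. These figures rest on an assumed half-life of 60 to 120 h and first-order decay; the one-day lean is illustrative, not a forecast.

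The importance is modest. The endpoint is secondary and descriptive, no hypothesis is tested, and the 15% level is background to the choice of dose, not a success criterion. The SAP leaves further specifications to the mock tables, figures and listings, which are not available here, but a model term and the time point to which its mean refers belong in the SAP.

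**What to change.** Keep the planned model and its mean. In SAP 5.4.1.4, pre-specify a second fit of the trough model only, not the recovery model:

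- Add x = time since last dose minus 7 days as a fixed linear covariate on log activity, keeping the random patient effect and all exclusion rules. Express x in days: hours divided by 24 where clock times exist for both dose and sample, otherwise the difference in days.
- Report the back-transformed mean and 95% CI at x = 0 (168 h) beside the planned estimate.
- Summarise the observed intervals among retained values (number, mean, SD, median, range), so that a reader can see whether timing leaned early or late.

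No new visits or samples are needed, because applying the 5-9 day rule already requires the interval. The cost is one extra fit on a descriptive endpoint and a somewhat wider interval when timing is off-centre. If intervals cluster tightly at 7 days, the slope will be poorly estimated and the two means should nearly coincide, which is itself reassuring. The SAP still names protocol version 1.0 as its basis while version 2.0 is current, so an update would be a natural occasion for the change.
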